9.4 STATISTICAL ANALYSES

9.4.1 GENERAL APPROACH

App utilization will be explored using descriptive statistics examining sums of weighing days, tracker wear, days of BG monitoring, and days tracking Red foods. Preliminary analysis of change over time in weight and A1c will be conducted using paired t-tests. Estimates of change on physiologic and psychologic variables, along with others in the literature, will be used to estimate effect sizes for the R01.

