4 STUDY DESIGN

4.1 OVERALL DESIGN

This project will test a weight loss intervention delivered through a mobile app for use in non-medication treated type 2 diabetics and pre-diabetics. The app is designed to integrate self-monitoring data from wireless scales and physical activity trackers, allow self-monitoring of foods through a Traffic Light diet approach, serve as a portal for feedback on behaviors and outcomes, and provide a platform for behavioral lessons. We will use the app coupled with in-person support to inform future versions.

We propose a single arm pilot trial testing the feasibility of a behavioral weight loss intervention for adults with type 2 diabetes or prediabetes. Participants will be instructed to decrease intake of Red foods, weigh daily, monitor BG using a CGM system, and gradually increase minutes of physical activity. This 12-week intervention is aimed at promoting improvements in diet quality consistent with recommendations for T2D, a decrease in energy intake, an increase in energy expenditure, and modest weight loss with a goal of improving glycemic control. Participants will meet weekly with a lifestyle counselor (interventionist) to review data on all behaviors, weight, and BG. The session will include feedback on progress, discussion of core content, problem solving and goal setting.

Participants will be given activity trackers (Fitbit Inspire) and wireless digital scales (Withings) to use for the duration of the study. Dietary behaviors will be monitored using an app that our research team has developed to track foods using the Traffic Light system. Assessments will occur at baseline and 12-weeks. Weight will be collected in the clinic on calibrated digital scales (Tanita) during in-person counseling sessions. Adherence measures will include self-monitoring and activity tracking, attendance at individual sessions and achievement of weekly diet and activity goals.

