5 STUDY POPULATION

5.1 INCLUSION CRITERIA

In order to be eligible to participate in this study, an individual must meet all of the following criteria:

- Currently age 20-65 years
- Diagnosed with type 2 diabetes or pre-diabetes
- Poor glycemic control ($\text{HbA1c} \geq 5.7\%$)
- BMI 25-40 kg/m²
- Own an iPhone with a data and text messaging plan
- Have home Wi-Fi access
- Have the ability to read, write, and speak English
- Not meeting the American College of Sports Medicine recommendation of 150 minutes of Moderate to Vigorous Physical Activity each week
- Ability to attend weekly visits at the UNC Weight Research Program clinic
- Can obtain primary care provider consent that appropriation is appropriate

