5.4 SCREEN FAILURES

Screen failures are defined as participants who consent to participate in this study but are not subsequently assigned to the study intervention or entered in the study. An example of a screen failure would be a participant who comes for the baseline assessment and does not meet the eligibility criteria (such as a BMI or HbA1c that is out of eligible range).

If the participant does not meet inclusion criteria, staff will inform the individual that they do not meet criteria for this particular study and ask if they would be interested in being contacted about future studies.

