Once an individual has been deemed potentially eligible to participate, they will be invited to the clinic for an orientation to the study where study staff will provide further information about the study and allow the potential participants to ask questions. This procedure, whereby potential participants have a chance to determine if the study is a good fit for them, has been effective in our past studies for high rates of retention. If the individual decides to participate, they will provide informed consent for participation. They will have their height, weight, and HbA1c measured and complete questionnaires. After completion of the baseline assessments, the in-person individual sessions will begin.

COVID-19 Modifications:

Orientation sessions were delivered via Zoom after March 15, 2020. If the individual decides to participate, study staff will send an email link to the Informed Consent Form for the study participant to review and electronically sign in REDCap. Once the consent is signed, the online study questionnaires will be deployed to the participant. Once questionnaires are complete, the participant will be scheduled to attend the baseline assessment visit at the clinic and to attend the kickoff session.

Incentives

Participants will receive \$15 for completing the baseline assessment and \$25 for completing the 12-week assessment. Participants who complete the 12-week assessment will be allowed to keep the Fitbit and scale.

The small incentives are meant to offset the time for completing the study questionnaires, transportation costs for coming to clinic for assessments, and to ensure that we get adequate follow-up data once the study has been completed by the participant. The Fitbit and scale are relatively affordable devices that are widely available to the general public.

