12 APPENDIX

Inclusion Criteria:

1. Currently age 20-65
2. BMI 25-50 kg/m²
3. Normal or impaired glucose as determined by HbA1c fingerstick (<6.5%)
4. Own an iPhone with a data and text messaging plan
5. Have home Wi-Fi access
6. Have the ability to read, write, and speak English
7. Not meeting the American College of Sports Medicine recommendation of 150 minutes of Moderate to Vigorous Physical Activity each week
8. Ability to attend weekly visits at the UNC Weight Research Program clinic for one month and weekly in-person, phone, or video call for an additional two months
9. Can obtain primary care provider consent that participation is appropriate

Exclusion Criteria:

1. Lost more than 10 pounds in the last 6 months
2. History of weight loss surgery
3. Currently participating in another physical activity or weight loss program or research study that may interfere with participation in this study
4. Currently meeting exercise recommendations of 150 minutes per week of moderate-to-vigorous physical activity
5. Currently pregnant, pregnant within the past 6 months, or planning to become pregnant within the next 4 months
6. Planning to relocate in the next 4 months

7. Pre-existing medical condition(s) that preclude adherence to an unsupervised exercise program, as determined by items endorsed on the PAR-Q (Physical Activity Readiness Questionnaire)
8. Diagnosis of diabetes
9. Taking medications to treat prediabetes
10. Report taking prescription or over the counter medication with a known impact on metabolism or weight
11. Current treatment for cancer
12. History of clinically diagnosed eating disorder
13. Diagnosis of schizophrenia or bipolar disorder
14. Hospitalization for a psychiatric diagnosis within the last year
15. Report a past diagnosis of or current symptoms of alcohol or substance dependence
16. Unwilling or unable to wear the CGM device continuously for the duration of the study
17. On dialysis

No exclusion criteria shall be based on race, ethnicity, or gender.

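### Under the Section 5.1 HbA1c criterion, one baseline fingerstick both admits the participant and serves as the 'before' value, so the uncontrolled HbA1c change is biased in expectation towards improvement

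*Combined protocol and SAP*

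**What the plan says.** - **Analysis.** Section 9.4.1: "Preliminary analysis of change over time in weight and A1c will be conducted using paired t-tests". Section 9.4.3 refers back to it for the secondary endpoints, of which HbA1c change is one. The same section says that estimates of change, together with published ones, will inform effect sizes for the R01.
- **Entry rule.** Section 5.1 lists "Poor glycemic control", defined as HbA1c of at least 5.7%, with no upper limit. It also requires a diagnosis of type 2 diabetes or pre-diabetes.
- **When the rule is applied.** Section 5.4 gives as an example of a screen failure someone who attends the baseline assessment and "does not meet the eligibility criteria (such as a BMI or HbA1c that is out of eligible range").
- **Measurement.** Section 5.5, on enrolment: "They will have their height, weight, and HbA1c measured and complete questionnaires". Section 8.1 describes one point-of-care fingerstick for HbA1c and no replicate, whereas weight and height are each measured twice.
- **Timing and control.** Section 4.1: "Assessments will occur at baseline and 12-weeks". The trial has a single arm.
- **Conflicting list.** Section 12 (Appendix) admits "Normal or impaired glucose as determined by HbA1c fingerstick (<6.5"%), which is an upper limit with no lower one, and excludes people with a diagnosis of diabetes.

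The documents do not mention regression to the mean, a separate qualifying reading or an adjustment for selection.

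**The concern.** An HbA1c reading is the person's underlying level plus biological and assay variation. If entry requires the reading to reach 5.7%, people near the limit whose reading is low by chance are turned away, and those whose reading is high by chance are kept. The average chance error among those enrolled is therefore positive at baseline, whereas at week 12 it averages zero. The expected paired difference is a fall even with no intervention effect, and there is no control arm from which to subtract it.

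The paired t-test takes zero change as its null value. Under this selection, zero effect does not correspond to zero expected change. At stake is a secondary endpoint and, more practically, the HbA1c effect size carried into the R01, since gathering preliminary data for that application is the pilot's stated purpose.

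**Working it through.** There is no figure in the plan to reproduce: Section 9.2 says the sample size was not derived statistically, and no HbA1c SD, alpha or target effect is given.

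**Inputs from the documents.** Lower limit 5.7% (Section 5.1); upper limit 6.5% (Section 12); n=20 (Synopsis); two time points and one arm (Section 4.1); reference HbA1c reductions of 0.17 and 0.27 points from the meta-analysis of glucose self-monitoring in Section 2.2.

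**Assumptions, because the documents give no values.** Mean true HbA1c of those tested, m = 5.7-6.2%; between-person SD, sb = 0.3-0.5; within-person SD (biology plus assay), sw = 0.10-0.25; normal distributions; two-sided 5% test.

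**Formulas, zero intervention effect.** Let st = √(sb² + sw²), z = (5.7 − m)/st and u = (6.5 − m)/st.
- Lower limit only: E[change] = −(sw²/st) · φ(z)/(1 − Φ(z))
- Upper limit only: E[change] = +(sw²/st) · φ(u)/Φ(u)
- Both limits: E[change] = −(sw²/st) · [φ(z) − φ(u)]/[Φ(u) − Φ(z)]

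**Central case (m = 5.8, sb = 0.4, sw = 0.2), lower limit only.**
- st = √(0.16 + 0.04) = 0.447
- z = (5.7 − 5.8)/0.447 = −0.224
- φ(z) = 0.389; 1 − Φ(z) = 0.588
- sw²/st = 0.04/0.447 = 0.0894
- E[change] = −0.0894 × 0.389/0.588 = −0.059 points

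This is 0.059/0.17 = 35% of the smaller reference reduction and 0.059/0.27 = 22% of the larger.

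**Over the whole grid.**

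| Entry rule | Expected change with no effect | Central case |
|---|---|---|
| At least 5.7% (Section 5.1) | −0.128 to −0.004 | −0.059 |
| Below 6.5% (Appendix) | +0.0005 to +0.061 | +0.011 |
| Both limits | −0.117 to +0.029 | −0.046 |

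Under the Section 5.1 rule the largest bias is at m = 5.7, sb = 0.3, sw = 0.25, and the smallest at m = 6.2, sb = 0.3, sw = 0.10.

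**Effect on the test.** Simulated paired t-tests with n=20, zero effect and entry at 5.7% or above; nominal chance of a significant fall 2.5%:

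| m, sb, sw | Chance of a significant fall |
|---|---|
| 5.7, 0.3, 0.2 | about 29% |
| 5.8, 0.4, 0.2 | about 15% |
| 6.0, 0.4, 0.2 | about 8-9% |
| 6.2, 0.4, 0.10 | about 3.5% |

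In the central case the mean change is nevertheless a rise in about 17% of null trials.

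**The case against.** **The size is assumed throughout.** The range of 0.004 to 0.13 is about 33-fold, and its low end is negligible. The central case implies that 1 − 0.588 = 41% of those tested fail at baseline, so 20/0.588 = about 34 people tested; nothing in the documents supports or excludes that. Entry also requires an existing diagnosis, and the online screener rejects people without pre-diabetes or diabetes. Either could lift the pool above the limit and shrink the bias. This stands, and is why only a range can be given. The population is unmedicated and includes pre-diabetes, however, so readings near 5.7% are plausible.

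**A stronger reading is tempting.** A reader might infer that the paired t-test will show an improvement even if the intervention does nothing. The documents do not support that. The bias is in expectation. In the central case most null trials (about 85%) show no significant fall, and some show a rise.

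**The direction is not settled.** The Appendix rule alone would give an apparent worsening, and with both limits the sign depends on the pool mean. This also stands: the improvement bias is conditional on Section 5.1.

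**The consequences are limited.** HbA1c is secondary, Section 9.1 states no hypotheses, and the analysis is called preliminary. Published estimates will also inform the R01, and Section 4.2 foresees a randomised successor whose between-group comparison would not carry this bias. In the central case the SD of change is about 0.27, so the standard error is 0.27/√20 = about 0.06, the same size as the bias. All true, but a bias of one standard error in a planning estimate is worth disclosing, and it affects the estimate whether or not the test is significant.

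**Conclusion.** The point holds conditionally. If the Section 5.1 limit is applied to the single baseline fingerstick, as Section 5.4 indicates, the uncontrolled HbA1c change is biased in expectation towards improvement, and the raw paired t-test is not centred on zero under no effect. The size cannot be fixed from the documents. It is 0.004 to 0.13 points on the stated assumptions, with 0.06 as one illustrative value rather than an estimate for this trial. All of this rests on assumed SDs, an assumed pool mean and normality. The matter is worth correcting because it bears on R01 planning; it does not undermine the pilot's feasibility aims, and nothing here concerns the primary weight endpoint.

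**What to change.** 1. Reconcile the HbA1c criteria in Section 5.1 and Section 12. Until that is done, neither the direction of the bias nor the right correction is defined.
2. Add to Section 9.4.1 that the numeric baseline HbA1c of everyone tested, including screen failures, is retained and used to estimate the mean and SD before selection. Section 8.1 currently promises only that reasons for ineligibility are kept for descriptive purposes.
3. Report the raw change together with a sensitivity range of the change corrected for regression to the mean. Use the formula that matches the reconciled limit or limits, for within-person SD 0.10 to 0.25. The lower-limit formula must not be used if an upper limit also applies. At mean 5.8 and between-person SD 0.4, the lower-limit correction runs from 0.016 to 0.089 points, so it must be shown as a range; there is no single corrected value.
4. State that the raw paired t-test is not centred on zero under no effect, and take the corrected range, not the raw estimate alone, into R01 planning.

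**Cost.** A short paragraph and one extra table, with no new measurement. Under a lower limit the HbA1c estimate becomes slightly less favourable. The correction depends on an assumed within-person SD and a normal pool, with the pool's mean and SD estimated from few people. Taking a second reading after qualification as the baseline would avoid these assumptions (simulated spurious change 0.00), but it costs a further fingerstick and works only for participants not yet enrolled.

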9.4.2 ANALYSIS OF THE PRIMARY EFFICACY ENDPOINT(S)

See 9.4.1

9.4.3 ANALYSIS OF THE SECONDARY ENDPOINT(S)

See 9.4.1

9.4.4 SAFETY ANALYSES

Safety endpoints will be analyzed as summary statistics during treatment and/or as change scores from baseline.

Each AE will be counted once only for a given participant), presented (e.g., expectedness, severity, frequency, and relationship of AEs to study intervention will be presented by System Organ Class (SOC) and preferred term groupings.

AE start date, stop date, severity, relationship, expectedness, outcome, and duration will be reported.

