Minimization of risk: Through instructions on usage of the CGM will be provided to the participant at the beginning of the study. Proper placement and care will be emphasized and, if irritation does occur, participants will be instructed to discontinue use of the sensor and alert the study staff.

5. Risk of finger stick: Approximately 3 drops of blood will be removed by finger stick. This is a standard method used to obtain blood for routine hospital laboratory tests. The participant may experience pain when the lancet goes into their finger. Other than this momentary pain, the discomfort of finger stick should be minimal. However, in about 10% of the cases a small amount of bleeding under the skin will produce a bruise (hematoma). A small scar may persist for several weeks. The risk of local infection is less than 1 in 1,000.

Minimization of risk: Staff are trained in the sanitary collection of blood using gloves, prepping the area with an alcohol swab, having the participant apply pressure to the finger after the finger stick and application of a bandage if needed.

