8 STUDY ASSESSMENTS AND PROCEDURES

8.1 EFFICACY ASSESSMENTS

Note: Refer to the Schedule of Activities 1.3 for the timing and frequency of assessments.

Screening and Orientation

Screening, orientation, and enrollment procedures are described in section 5.5. At each point, study staff will confirm eligibility, as described. The participant has the choice to discontinue participation at any point. If participation is discontinued by staff or the participant, screening information will be held for the duration of the study and identifiers will be destroyed after the study is complete. Reasons for ineligibility will be retained for descriptive purposes.

Physical Measurements

Weight (kg) (primary outcome): Participants will be weighed wearing shorts and without shoes using a calibrated digital Tanita scale. Trained study staff will conduct these measurements following a standardized protocol. Two measures will be completed and the average of the two will be used. If the difference between the two measures exceeds 0.2 kg, a third measure will be taken.

Height (cm): Height will be measured at baseline using a wall-mounted stadiometer (Country Technology Inc, WI). Two measures of height will be taken and the average of the two will be used. If the two measures are not within 0.5 cm, a third measurement will be taken

BMI: Height and weight will be used to calculate BMI.

HbA1c will be measured with a fingerstick and analyzed on a point of care unit (Afinion Alere).

REDCap questionnaires:

Demographics. Participants will provide demographic information at baseline. They will provide age, gender, race/ethnicity, weight, and smoking history. (Baseline only)

Diabetes Specific Locus of Control.

We will administer an 18-item questionnaire consisting of three domains measuring diabetes-specific internal locus of control, powerful other locus of control, and chance locus of control (39).

Diabetes Obstacles Questionnaire. This is a diabetes-related quality of life questionnaire consisting of 30 items using a 5-point Likert-scale addressing social, psychological, cognitive, and behavioral obstacles (40).

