8.3.3.2 RELATIONSHIP TO STUDY INTERVENTION

All adverse events (AEs) will have their relationship to study procedures, including the intervention, assessed by an appropriately-trained clinician based on temporal relationship and his/her clinical judgment. The degree of certainty about causality will be graded using the categories below.

- **Related** – The AE is known to occur with the study procedures, there is a reasonable possibility that the study procedures caused the AE, or there is a temporal relationship between the study procedures and the event. Reasonable possibility means that there is evidence to suggest a causal relationship between the study procedures and the AE.
- **Not Related** – There is not a reasonable possibility that the study procedures caused the event, there is no temporal relationship between the study procedures and event onset, or an alternate etiology has been established.

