8.3.4 TIME PERIOD AND FREQUENCY FOR EVENT ASSESSMENT AND FOLLOW-UP

The occurrence of an adverse event (AE) or serious adverse event (SAE) may come to the attention of study personnel during study assessment visits and individual coaching sessions.

All AEs, not otherwise precluded per the protocol, will be captured on the appropriate adverse events form. Information to be collected includes event description, time of onset, clinician's assessment of severity, relationship to study procedures (assessed only by those with the training and authority to make a diagnosis), and time of resolution/stabilization of the event. All AEs occurring while on study will be documented appropriately regardless of relationship. All AEs will be followed to adequate resolution.

Any medical or psychiatric condition that is present at the time that the participant is screened will be considered as baseline and not reported as an AE. However, if the study participant's condition deteriorates at any time during the study, it will be recorded as an AE.

Changes in the severity of an AE will be documented to allow an assessment of the duration of the event at each level of severity to be performed. Documentation of onset and duration of each episode will be maintained for AEs characterized as intermittent.

[name] will record events with start dates occurring any time after informed consent is obtained until 7 (for non-serious AEs) or 30 days (for SAEs) after the last day of study participation. At each study visit, the study team will inquire about the occurrence of AE/SAEs since the last visit. Events will be followed for outcome information until resolution or stabilization.

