10.2 ADDITIONAL CONSIDERATIONS

During the 12-week study, participants will monitor their blood glucose using the Abbott Freestyle Libre Continuous Glucose Monitoring system. For the CGM, a representative of the device manufacturer (Abbott) will train research staff to instruct study participants on the use of the device. The device is commercially available and measures blood sugar without the need for finger sticks. It involves placement of a sensor on the upper arm and use of a scanning device to "read" the sensor. Use of the device is considered 'off-label' for individuals without diabetes.

The study interventionists in this study are trained in behavioral weight control, have served this role in weight control interventions in the lab for 5 – 15 years, and are Master's or PhD level in Health Behavior, Nutrition (and Registered Dietitian), or Exercise Physiology.

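### The adverse-event table is labelled as relationship to the study intervention, but the only rating collected covers all study procedures, including the HbA1c fingerstick

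*Combined protocol and SAP*

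**What the plan says.** Section 9.4.4 (Safety Analyses) states that the "relationship of AEs to study intervention will be presented by System Organ Class (SOC) and preferred term groupings", with each event counted once per participant.

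Section 8.3.3.2 defines the rating. Its heading refers to the study intervention, but its text is wider: "All adverse events (AEs) will have their relationship to study procedures, including the intervention, assessed by an appropriately-trained clinician". There are two categories, Related and Not Related, and both are worded in terms of study procedures. Related begins "The AE is known to occur with the study procedures, there is a reasonable possibility that the study procedures caused the AE" and can also be met by a temporal link alone.

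Section 8.3.4 lists what is collected for each event. The only relationship item is "relationship to study procedures (assessed only by those with the training and authority to make a diagnosis", to continue inside its bracket. The same section asks for a description and onset time for every event, requires documentation whatever the relationship, and starts recording at informed consent.

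On the fingerstick:
- Section 2.3.1 gives its risk: "in about 10% of the cases a small amount of bleeding under the skin will produce a bruise (hematoma", again inside an open bracket.
- Section 8.1 gives its purpose: "HbA1c will be measured with a fingerstick and analyzed on a point of care unit (Afinion Alere".
- Section 4.1 gives the timing: "Assessments will occur at baseline and 12-weeks".
- Section 10.2 says that the glucose monitor used in the intervention "measures blood sugar without the need for finger sticks".
- Section 5.5 places the first coaching session after the baseline assessments.

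**The concern.** The table is to show one quantity and the form collects a broader one. With a single relationship item per event, the 9.4.4 table can only be filled from the all-procedures rating, so harm caused by the research assessments would appear under an intervention label.

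The study has one arm. There is no control group against which to judge which events the intervention caused, so the attribution rating is the main means of separating intervention harm from other events. That is why the label should match what was rated, even in a small pilot.

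**Working it through.** The plan states no figure for this point, so there is nothing to reproduce. The check is a comparison of sections, followed by a bound on the size.

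**Step 1: scope of each item**
- Clinician's rating (8.3.3.2): all study procedures, with the intervention as one part.
- AE form item (8.3.4): study procedures.
- Reported output (9.4.4): study intervention.

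The first two agree with each other and are wider than the third. No separate intervention-only rating is described.

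**Step 2: is there a procedure outside the intervention that can cause an event?** Yes. The fingerstick serves the HbA1c assessment (8.1), and the intervention's glucose monitoring does not need it (10.2). Bruising is a listed risk (2.3.1), so a recorded bruise meets the first criterion for Related.

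**Step 3: the clearest case.** Events are recorded from consent (8.3.4) and sessions begin after baseline assessments (5.5). A bruise from the baseline stick comes before any intervention session. It would still be rated Related and then shown as related to the intervention.

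**Step 4: how large could this be?** Inputs: n = 20 (section 1.1, objectives), p = 0.10 per stick (2.3.1), s = 2 sticks (4.1 and 8.1). Assumptions: sticks are independent, both visits take place, and every bruise is recorded.
- Expected bruises: n × s × p = 20 × 2 × 0.10 = 4.0.
- Chance that a participant has at least one: 1 − (1 − p)^s = 1 − 0.9² = 0.19.
- Expected participants under the once-per-participant rule: 20 × 0.19 = 3.8.
- Chance of at least one such participant: 1 − 0.81^20 = 0.985.

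**Step 5: relaxing the assumptions**
- One stick counted: 20 × 0.10 = 2.0 participants; chance of at least one, 1 − 0.9^20 = 0.878.
- Two sticks, half of bruises recorded: 20 × (1 − 0.95²) = 1.95 participants.
- Two sticks, a quarter recorded: 20 × (1 − 0.975²) = 0.99 participants.
- None recorded: 0.

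The recording fractions are illustrative, because the documents give none.

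**Step 6: effect on a participant-level rate.** Let q be the share of bruised participants who already have another related event. The addition to the share with any related event is 0.19 × (1 − q). It equals 19 percentage points only if q = 0, and it falls to zero as q approaches 1. The documents give no value for q.

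**The case against.** The strongest reply is that this is loose wording. The section that defines the rating carries the narrower term in its heading and the wider one in its text, and the 9.4.4 sentence reads like unfinished template text. That explains how the mismatch arose but does not resolve it: the operative definition and the form item both use the wider scope.

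Several limits on the consequence do stand:

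- **Tracing is possible.** A reader might infer that assessment bruises could never be separated afterwards. That is true of the rating taken alone, but not of the record. Section 8.3.4 asks for a description and onset time, and 9.4.4 reports start dates. With about 20 participants, most bruises could be traced.
- **Preferred terms help somewhat.** A reader might also suppose that finger bruises would merge with bruises at the sensor site. No section lists bruising as a risk of the glucose monitor; section 2.3.1 names skin irritation from the adhesive. No coding dictionary is specified, so how terms would group is unknown.
- **The 10% is a risk description,** not a rate of recorded adverse events. Minor bruises may go unreported.
- **Both sticks may not count.** Section 9.4.4 speaks of summaries during treatment. If that governs the event table, the baseline stick drops out. The Medical Events questionnaire is given at the same 12-week assessment as the second stick, and no later scheduled contact is described, although the window for non-serious events runs 7 days beyond participation. Section 10.4 records a period when in-person assessments were suspended.
- **Nothing formal depends on the rating.** There are no hypotheses (9.1), no interim analysis (9.4.6) and no pre-specified criteria for closing the study (10.1.2).

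**Conclusion.** The mismatch is real: a rating made against all study procedures is to be presented as relationship to the intervention, and a recorded fingerstick bruise would be mislabelled as a result. That consequence is an inference from sections 8.3.3.2, 8.3.4 and 9.4.4 read together; no section states it.

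The size lies between zero and a ceiling of about 3.8 of 20 participants. The ceiling requires the 10% to hold for each of two independent sticks, both visits to take place, every bruise to be recorded and nobody bruised to have another related event. It would be tempting to say that the intervention-related rate is overstated by 5 to 19 percentage points. The documents do not support that range: the lower end rests on an assumed 25% recording fraction, and the upper end is the ceiling, not an estimate.

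It would also go too far to say that a wrong harm rate will be carried into the larger trial. Section 9.4.1 carries forward changes in physiologic and psychologic variables, and no section says that an intervention-related event rate will be used. The effect is confined to the labelling and interpretation of the safety table. It is a small point, but a definite one and worth correcting.

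**What to change.** Either of two changes removes the error.

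1. **Preferred.** Record two attributions on the AE form: to the intervention (glucose monitor wear, activity, diet, self-weighing, app) and to assessment procedures (fingerstick, clinic measurements). Use only the first for the 9.4.4 table on relationship to the intervention, and show the second separately. Keep the combined judgement for reporting to the IRB. The cost is one extra tick-box and one extra table column.

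2. **Minimum.** Keep the single rating, retitle the 9.4.4 output as relationship to study procedures (intervention included), and use the same term in 8.3.3.2, its heading, 8.3.4 and 9.4.4. The cost is a retitle. The table would then be correctly labelled, but it would not isolate intervention harm.
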